### Secondary Objective

The secondary objectives are:

#### Safety

##### Acute (30 days post procedure):

- The assessment of peri-procedural events

##### Midterm (6 months):

- Assessment of renovascular safety as measured by new renal artery stenosis or aneurysm at the site of ablation
- Renal function change based on eGFR

##### Long term (2 and 5 years):

- Assessment of renovascular safety as measured by new renal artery stenosis or aneurysm at the site of ablation
- Renal function change based on eGFR

#### BP reduction

- Change in Ambulatory Blood Pressure parameters at 6 months
- Change in office Diastolic Blood Pressure at 6 months
- Percentage of subjects achieving office Systolic Blood Pressure < 140 at 6 month visit
- Change in Office and Ambulatory Blood Pressure parameters at 12, 24, 36, 48, 60 months post denervation

## 3.3 Investigational Type

This is a post market, prospective, multicenter, non-randomized, single arm study of the EnligHTN™ Renal Denervation System. Approximately 500 subjects with uncontrolled hypertension will undergo renal artery ablation at approximately 40 investigational sites located internationally and will be followed up to five (5) years post procedure.

## 3.4 Patient Population

The patient population enrolled in this investigation will consist of male and female patients 18 years of age or older that meet all of the specified inclusion criteria and none of the specified exclusion criteria (Section 3.5).

### 3.5 Patient Screening

All patients treated at the investigational site can be screened by a member of the investigational team. This team member needs to be trained on the Clinical Investigational Plan (CIP) and the task of subject screening needs to be delegated in writing to this team member by the Principal Investigator.

The patient will be given ample time to ask questions and to understand the risks of being a part of this investigation. In case the patient agrees to participate, a duly signed and dated Patient Informed Consent (PIC) will be obtained.

### 3.6 Inclusion and Exclusion Criteria / Point of Enrollment

A patient, who meets all of the inclusion criteria, and none of the exclusion criteria, is eligible to participate in this investigation. A patient becomes a subject once he/she has been fully informed about the investigation, has agreed to participate, signed & dated the PIC and therefore has been enrolled in the investigation. (Refer to section 5.2 for the Informed Consent Process)

Once enrolled, a subject is expected to comply with the scheduled visits and required activities according to the CIP. The subject should undergo the renal denervation procedure within 30 days of the baseline visit but must be no longer than 90 days from baseline.

All subjects enrolled in the clinical investigation (including those withdrawn from the clinical investigation or lost to follow-up) shall be accounted for and documented in the Patient Identification Log, assigning an identification code linked to their names, alternative identification or contact information. Because subject privacy and confidentiality of data must be maintained throughout the clinical investigation, this log will only remain on site.

This log shall be kept up to date throughout the clinical investigation by the Principal Investigator or his/her authorized designee.

#### 3.6.1 Inclusion Criteria

- Subject is  $\geq 18$  years of age at time of consent
- Subject must be able and willing to provide written informed consent
- Subject must be able and willing to comply with the required follow-up schedule
- Subject has office Systolic Blood Pressure  $\geq 140$  mmHg at confirmatory visit
- Subject has a daytime mean Systolic Ambulatory Blood Pressure  $> 135$  mmHg within 90 days prior to procedure
- Subject has established hypertension (diagnosed  $\geq 12$  months prior to baseline) and is on a guideline based drug regimen at a stable and a fully tolerated dose consisting of  $\geq 3$  anti-hypertensive medications (including 1 diuretic), or subject has documented drug intolerance to 2 or more of the 4 major classes of anti-hypertensives (ACE/ARB, Calcium Channel Blockers, Beta Blockers, or diuretic) and is unable to take 3 anti-hypertensive drugs.

#### 3.6.2 Exclusion Criteria

- Subject has significant renovascular abnormalities such as renal artery stenosis  $> 30\%$

- Subject has undergone prior renal angioplasty, renal denervation, indwelling renal stents, and/or abdominal aortic stent grafts
- Subject has hemodynamically significant valvular heart disease as determined by Study investigator
- Subject has a life expectancy less than 12 months, as determined by the Study Investigator
- Subject is participating in another clinical study which has the potential to impact their hypertension management (pharmaceutical / device / homeopathic)
- Subject is pregnant, nursing, or of childbearing potential and is not using adequate contraceptive methods
- Subject has active systemic infection
- Subject has renal arteries with diameter(s) < 4 mm in diameter
- Subject has an estimated GFR <15 mL/min per 1.73 m^2 using the Modification of Diet in Renal Disease (MDRD) formula
- Subject had a renal transplant or is awaiting a renal transplant
- Subject has blood clotting abnormalities

### **3.7 Procedural Exclusions**

Subjects who have been enrolled in the clinical investigation and the procedure was started but do not have the EnligHTN™ Renal Denervation System enter their body, due to their anatomy, circumstances related to the procedure, or physician judgment will be classified as procedurally excluded. The reason for the procedural exclusion will be documented on the Procedural CRF. The subject will return for a 1 month follow up visit and have a physical assessment and office blood pressure completed.

### **3.8 Expected duration of the Investigation**

The expected duration of the investigation will be approximately six (6) years.

### **3.9 Expected duration of each subject's participation**

The expected duration of each subject enrolled in the clinical investigation will be five (5) years.

### **3.10 Number of subjects required to be included in the Investigation**

Enough subjects will be enrolled to have approximately 500 subjects undergo the renal denervation procedure in the investigation. Procedurally excluded subjects will not count towards the expected number of treated subjects.

### **3.11 Estimated time needed to select this subject population**

The estimated time needed to enroll the number of subjects will be approximately 8 months.

### **3.12 Devices Used**

The EnligHTN™ Renal Denervation System is designed to deliver radiofrequency (RF) energy to the renal nerves to achieve targeted denervation. The system consists of the EnligHTN™ RF Ablation Generator (generator), the EnligHTN™ Renal Artery Ablation Catheter (ablation catheter), and the EnligHTN™ Guiding Catheter (optional).

The following market approved St. Jude Medical devices to be first used in this investigation are:

---

SJM CONFIDENTIAL AND PROPRIETARY

© 2012 – St. Jude Medical Cardiovascular Division: All rights reserved. No portion of this work may be reproduced in whole or in part without the express written permission of St. Jude Medical Cardiovascular Division.  
Clinical Investigational Plan: EnligHTN II

### **3.12.1 EnligHTN™ Renal Artery Ablation Catheter**

The EnligHTN™ Renal Artery Ablation Catheter is a single use device that has an expandable electrode basket with four Platinum-Iridium (Pt-Ir) ablation electrodes. The electrodes deliver low-level radiofrequency energy to the renal arteries through a percutaneous vascular access site. The distal segment of the ablation catheter is deflectable to assist in proper basket positioning. The handle is used to actuate the expansion and relaxation of the basket, and to actuate the deflection of the ablation catheter at the distal end. The ablation electrodes and the tip are radiopaque to provide visualization under fluoroscopy.

### **3.12.2 EnligHTN™ RF Ablation Generator**

The EnligHTN™ RF Ablation Generator delivers RF energy to the EnligHTN Renal Artery Ablation Catheter using a proprietary algorithm developed to produce a consistent, transmural ablation pattern during the renal denervation procedure.

### **3.12.3 EnligHTN™ Guiding Catheter (optional)**

The EnligHTN™ Guiding Catheter system is comprised of two (2) components: a guiding catheter and a dilator. The guiding catheter is constructed of three (3) components: a polytetrafluoroethylene (PTFE) liner, a stainless steel braid, and a multi durometer polymer jacket. The proximal end of the catheter terminates in a hemostasis hub and a hemostasis valve. An extension tube and 3-way stopcock valve is attached to the sideport of the hemostasis hub. The distal end of the catheter terminates in a renal curve with a radiopaque marker embedded in the polymer jacket approximately 2 mm from the catheter tip. The dilator is a polymer tube with an inside diameter sized for guidewire clearance. The proximal end terminates in a snap fitting to mate with the guiding catheter hemostasis hub. The distal end is tapered to facilitate insertion through an introducer sheath.

## **3.13 Intended Use**

The ablation catheter is indicated for use in renal denervation procedures for the treatment of hypertension.

[figure not shown]
## 4 Procedures

Table 1: Data/CRF Collection

Visit	Enrollment / Baseline	Confirmatory	Procedure	Discharge <72 hrs	1M ±14d	6M ±30d	12M ±60d	24M ±60d	36M ±60d	48M ±60d	60M ±60d
PIS & PIC	X										
Inclusion/Exclusion	X	X-review for changes									
Medical History	X	X-review for changes									
Office Blood Pressure	X	X		X	X	X	X	X	X	X	X
Physical Assessment	X	X-review for changes		X	X	X	X	X	X	X	X
24-h Ambulatory Blood Pressure	X-performed w/in 90 days of procedure	X-repeat if there are medication changes				X	X	X	X	X	X
Discharge Blood Pressure				X*							
***Echocardiography (TTE)		X			X	X		X			X
NYHA Assessment	X				X	X		X			X
Serum creatinine		X				X	X	X			X
Estimated GFR		X				X	X	X			X
Hemoglobin A1c		X				X					
Fasting Glucose		X				X					
Fasting Insulin		X				X					
Urine albumin-to-creatinine ratio		X				X		X			X
Medications Log	X	X-review for changes		X	X	X	X	X	X	X	X
Quality of Life questionnaire		X			X	X		X			X
Renal Artery Anatomy Evaluation		X – if not performed w/in 90 days	X			X		X			X
Pregnancy Test (urine / blood)		X									
Renal Denervation Procedure			X								
Adverse Event	**	**	**	**	**	**	**	**	**	**	**
CIP Deviation	**	**	**	**	**	**	**	**	**	**	**
Withdrawal/Termination			**	**	**	**	**	**	**	**	X
(*) monitored every 4 hours post procedure until discharge, or for a maximum of 24 hours (**) as applicable (***) Echo will be performed at 6 preselected sites											

SJM CONFIDENTIAL AND PROPRIETARY

© 2012 – St. Jude Medical Cardiovascular Division: All rights reserved. No portion of this work may be reproduced in whole or in part without the express written permission of St. Jude Medical Cardiovascular Division.  
 Clinical Investigational Plan: EnligHTN II

SJM CONFIDENTIAL AND PROPRIETARY

## 4.1 Enrollment/Baseline Visit

Prior to enrollment in the clinical investigation, site personnel will evaluate potential candidates by reviewing the patient medical records against the inclusion and exclusion criteria. It is expected that the medical records will contain adequate and accurate information to determine if the patient meets these criteria.

If a patient meets all inclusion criteria and does not meet any of the exclusion criteria, the patient shall be eligible for the investigation.

If the patient agrees to participate, the study site personnel shall follow the informed consent process set forth in Section 5.2 and obtain the signature and date from the patient on the approved Patient Informed Consent (PIC) form (previously approved by Ethics Committee and the Sponsor). If the patient does not sign and date the Patient Informed Consent (PIC), they cannot participate in the investigation. No further CIP required activities are allowed.

A patient becomes a subject once he/she has been fully informed about the investigation, has agreed to participate, signed & dated the PIC and therefore has been enrolled in the investigation.

NOTE: As soon as the subject signs the Patient Informed Consent, adverse events need to be reported according to the guidelines mentioned in Section 5.3.

The EC should be notified appropriately about any CIP deviations with regards to obtaining informed consent.

If new information becomes available during the clinical study that can significantly affect a patient's future health and medical care, that information will be provided to the patient(s) in written form.

The following information will be collected at the baseline visit either from hospital records or through patient interaction documented in the hospital records. All baseline activities are performed after the patient is enrolled in the investigation. Tests and procedures required at baseline can be completed within 90 days of enrollment but must be completed prior to procedure.

### 4.1.1 Medical History

A complete medical history of the subject will be reviewed and recorded including:

- Hypertension, renal, cardiovascular, neurological, obstructive sleep apnea, hyperlipidemia, diabetes (Type I and II), smoking, thyroid disease, liver disease, chronic obstructive pulmonary disease, and alcohol consumption

#### **4.1.2 Physical Assessment**

The subject will have a physical assessment recording at the baseline visit to capture the following:

- Age
- Gender
- Height (only at baseline)
- Weight

#### **4.1.3 Office Blood Pressure**

Office Blood Pressure measurements will be recorded as the average Blood Pressure of three measurements. If there is a change in medication after the office Blood Pressure assessment is completed an additional set of office Blood Pressure measurements is required to determine eligibility.

Measurements should be taken according to Standard Joint National Committee VII Guidelines / ESC and ESH Guidelines, refer to Appendix A for Office Blood Pressure instructions.

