### **4.2 Two Week Screening Period**

#### **4.2.1 Medication Regimen Monitoring (≥14-Day Period)**

The anti-hypertensive drug regimen of the subject will be monitored for a period of at least 14 days at baseline. Medication logs will be provided for the subject to record their daily anti-hypertensive drug regimen during the monitoring period. Upon the completion of the monitoring period (≥14 days), the subject will return to the study center with the medication logs for the continued baseline evaluation.

The medication log will be reviewed to assess the subject's compliance with their current medication regimen. The clinical investigation does allow the inclusion of subjects that are not on guideline based therapy due to intolerance. Intolerance to medications is defined as a relative or an absolute contraindication to an anti-hypertensive medication. This assessment will be left to the discretion of the Study Investigator.

It is recommended that the subjects maintain their enrollment anti-hypertensive regimen for a minimum of 180 days post procedure unless clinically necessary for changes to occur.

Investigators will urge subject compliance to prescribed medical regimen at the onset of the 14 day monitoring period and throughout the trial. If the subject is non-compliant without medical rationale, the subject may be excluded.

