#### **4.2.2 Ambulatory Blood Pressure**

To ensure proper patient selection for inclusion in the study subjects must have a daytime mean Ambulatory Blood Pressure (ABP) measurement of > 135 mmHg within 90 days prior to procedure.

If there is a change in medication after ABP assessment an additional ABP assessment is required to determine eligibility. In addition to the daytime mean ABP, the night time mean, and 24 hour average ABP value will be collected. When using ABP ensure that at least two measurements per hour are taken during the person's usual waking hours (for example, between 08:00 and 22:00) and 1 measurement per hour are taken during the person's usual night time hours. The average value of at least 14 measurements taken during the person's usual waking hours should be used for calculation of mean daytime value.

Measurements should be taken according to Standard Joint National Committee VII Guidelines ESC and ESH Guidelines, refer to Appendix B for 24 Hour Ambulatory Blood Pressure instructions.

The ABP can be taken during the two week screening period but must be repeated if there are medication changes. .

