#### **4.3 Confirmatory Visit**

After the two week screening period the subject will return to the Study Center for the confirmatory visit.

The following items will be reviewed or performed at the confirmatory visit to ensure there have been no changes prior to moving forward with the EnligHTN Renal Denervation procedure.

- Inclusion / exclusion criteria
- Medication logs
- Medical history & physical assessment
- Office Blood Pressure measurements will be recorded as the average Blood Pressure of three measurements
- Review of daytime mean Systolic Ambulatory Blood Pressure (must be repeated if there are medication changes)

If the subject does not meet eligibility after baseline and 2 week screening period they may be re-evaluated. The Office Blood Pressure, Medication log and the Ambulatory Blood Pressure will need to be repeated if it is determined the subject could be re-evaluated.

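### A drug change late in screening can be followed at once by the qualifying blood pressure readings, so drug effect still to come can enter the 6-month change

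*Combined protocol and SAP*

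**What the plan says.** **Entry.** Section 3.6.1 requires that the subject "is on a guideline based drug regimen at a stable and a fully tolerated dose consisting of" at least three antihypertensives including a diuretic, with an alternative for documented intolerance. It gives no duration or definition for a stable dose. The qualifying office systolic pressure is the one at the confirmatory visit.

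**Monitoring.** Section 4.2.1: "The anti-hypertensive drug regimen of the subject will be monitored for a period of at least 14 days at baseline". It does not say that a change of drugs restarts this period.

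**After a change.** For office pressure, Section 4.1.3 says "an additional set of office Blood Pressure measurements is required to determine eligibility". For ambulatory pressure, Section 4.2.2 says "If there is a change in medication after ABP assessment an additional ABP assessment is required to determine eligibility". Section 4.3 and Table 1 also ask for the ambulatory recording to be repeated. None of these gives a waiting time.

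**Confirmatory visit.** Section 4.3 reviews the entry criteria, medication logs and history "to ensure there have been no changes prior to moving forward with the EnligHTN Renal Denervation procedure". For a subject found ineligible who may be reconsidered, it adds: "The Office Blood Pressure, Medication log and the Ambulatory Blood Pressure will need to be repeated if it is determined the subject could be re-evaluated".

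**Analysis.** Section 7.4.1 takes each subject's office systolic change from baseline to 6 months, then the mean and standard deviation. There is no control arm (Section 7.1) and no adjustment for medication. The text does not say whether baseline is the enrollment, confirmatory or repeat reading.

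**The concern.** The rules for a medication change treat a fresh reading as enough to settle the blood pressure criteria. They do not ask whether the new regimen has had time to act. If a drug is started or increased shortly before the repeat, pressure may still be falling when it is taken. The reading is then too high as a pre-procedure value, and the later part of the drug effect appears as change after denervation. Without a control arm, the result cannot separate the two.

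The plan is also uneven. A screen failure who is reconsidered must repeat the medication log. A subject whose drugs have just changed, but whose repeat readings still qualify, need not.

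At stake are the primary 6-month office systolic result, the ambulatory results and, to a lesser degree, group assignment, which uses office systolic thresholds of 160 and 140 mmHg (Section 4.4).

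**Working it through.** The plan states no effect size, power or test (Section 7.2), so there is no design figure to reproduce. The check is mainly textual, with an illustration of size.

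**Step 1: who is affected, taking the rules together**

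- *Change early in screening.* The confirmatory office reading comes after at least 14 days, so much of that period may already have passed on the new regimen. Section 4.2.2 gives no such spacing for the repeat ambulatory recording.
- *Change late in screening, drug criterion already met.* The office set and the ambulatory recording are repeated. If both qualify, nothing requires a wait or a new log.
- *Drug criterion not met at the confirmatory visit.* The subject is ineligible and, if reconsidered, repeats the log.

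The gap is the second case and, for ambulatory pressure only, part of the first.

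**Step 2: shift in the mean change**

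Shift = p × E × r, where p is the share of subjects intensified in screening, E the full drug effect and r the fraction still to come at the baseline reading. All three are assumptions: p = 5% to 20%, E = 5 to 10 mmHg, r = 30% to 100%.

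- Low: 0.05 × 5 × 0.3 = 0.075 mmHg
- High: 0.20 × 10 × 1.0 = 2.0 mmHg
- In the affected subjects alone (E × r): 5 × 0.3 = 1.5 mmHg to 10 × 1.0 = 10 mmHg

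For a drug reduction the sign reverses.

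**Step 3: if baseline means the enrollment reading**

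That reading precedes the change, so r = 1. The shift is 0.05 × 5 = 0.25 mmHg to 0.20 × 10 = 2.0 mmHg. Delaying the repeat readings would not remove it, so the baseline must be named as well.

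**Step 4: scale**

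With an assumed standard deviation of change of 16 to 25 mmHg, the 95% half-width is 1.96 × SD / √n:

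| n | SD 16 | SD 25 |
|---|---|---|
| 500 | 1.4 mmHg | 2.2 mmHg |
| 50 (minimum, Groups B and C) | 4.4 mmHg | 6.9 mmHg |

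The shift thus runs from negligible to about the overall sampling error. Enrolling more subjects would not shrink it. Against the office systolic falls of about 25 to 28 mmHg cited in the Background, it is about 0.3% (0.075/28) to 8% (2.0/25).

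**Step 5: does the plan's own period fit?**

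A change at the earliest confirmatory visit plus a second monitoring period gives 14 + 14 = 28 days. Section 3.6 sets a 30-day target and a 90-day limit from the baseline visit to the procedure.

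**The case against.** A reader might infer that the plan merely repeats a reading and admits subjects who are not on a stable dose. The documents do not support that. The repeat is necessary, but nowhere is it called sufficient, and nothing waives the stable-dose criterion. Criteria and logs are reviewed again at the confirmatory visit. An investigator who reads the criterion strictly would not proceed the day after a change.

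A reader might also picture a third drug being added at the confirmatory visit to bring someone in. A subject on two drugs without the documented intolerance fails the criterion on arrival and falls under re-evaluation, where the log is repeated. Early changes may already have about 14 days before the qualifying office reading, and a drug reduction biases the result downward. The study is descriptive, and the size rests wholly on assumed inputs.

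All of this stands, and it narrows the point. It does not close it. Reviewing an undefined requirement gives a site nothing to apply, and the repeat rules presuppose that a subject with changed drugs may still be eligible. The repeated log reaches only those who fail and are reconsidered. A descriptive mean is shifted as much as a tested one.

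**Conclusion.** The concern holds in a limited form. A subject who already meets the drug criterion and has a late change in screening can qualify on repeat readings with no minimum time on the new regimen and no new log. An intensification would then add to the reported 6-month fall, and a reduction would hide part of it.

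The overall shift is about 0.1 to 2 mmHg under the stated assumptions, and 1.5 to 10 mmHg among affected subjects. The documents supply none of the inputs. They therefore do not support saying that the primary result is materially biased, only that the rules leave the route open and the analysis would not reveal it. It should be corrected because the remedy is cheap and uses the plan's own procedures.

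**What to change.** - **Screening.** Reconcile Sections 3.6.1, 4.1.3, 4.2.1, 4.2.2, 4.3 and Table 1. An antihypertensive change in screening should go through the existing 4.2.1 monitoring period and 4.3 re-evaluation route before the qualifying office and ambulatory readings are taken. State what a stable dose means for this purpose. The documents do not show that 14 days captures a drug's full effect, so this narrows the gap without guaranteeing that it closes.
- **Baseline.** In Section 7.4.1, name the qualifying office reading as the analysis baseline. Without this, the first change may not remove the bias.
- **Sensitivity analysis.** Repeat the primary summary excluding subjects whose antihypertensives changed between enrollment and 6 months, using the medication logs and the follow-up data of Section 4.8.2. Later changes may depend on response, so this belongs beside the main result and does not replace it.
- **Regimen wording.** Section 4.2.1 recommends keeping the enrollment regimen after the procedure, but enrollment is the signing of consent, before screening. The sponsor should reconcile this with regimens changed in screening; which regimen applies is a clinical matter for the sponsor.

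**Cost.** Protocol wording and one extra table. About two weeks' delay for a minority: 28 days at the earliest leaves two days against the 30-day target but is well inside the 90-day limit. A few subjects may no longer qualify.
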